## 16. STATISTICAL ANALYSIS PLAN

To assess differences in clinical and demographic variables of the patients allocated to the two study groups, independent samples t test or Mann–Whitney U test will be used for quantitative variables. For categorical variables, Chi-square test or Fisher's exact test will be used.

Outcome analysis will be performed using both an intention to treat analysis and a per-protocol analysis.

The overall impact of the intervention on the primary and secondary outcomes will be assessed considering both the results at the 12-week assessment as well as change from baseline.

Differences between interventions will be evaluated using independent samples t test or Mann–Whitney U test. For non-normally distributed variables, the magnitude of the difference in the medians will be assessed using Hodges-Lehman estimator. Additionally, a repeated measures ANOVA will also be performed, with group as an independent factor and time as a within-subjects factor. When necessary, logarithmic transformation will be performed to obtain normally distributed variables. In all analysis, a significant level of 0.05 will be considered.

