## 6. STUDY HYPOTHESIS

The digital program will be associated with at least the same outcomes as conventional PT.

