### 8. STUDY OUTCOMES

#### 8.1 Primary Outcome

Impact on functional disability measured through the Oswestry Disability Index score (patient reported outcome measure) between baseline and 8 weeks.

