## **9. SAMPLE SIZE ESTIMATION**

Sample size estimation calculations were performed taking into consideration the primary outcome measure – The Oswestry Disability Index (ODI). In the absence of similar studies, the calculations were made considering the study by Stankovic et al. (2012). This was a large study (n=160 patients), which compared two different rehabilitation protocols for CLBP and which used the same primary outcome as the present study. In this study, the standard deviation of the ODI at baseline was 17.83 points. A Minimal Clinically Important Change (MCIC) of 10 points was considered, based on the study by Ostelo et al. Considering a power of 80% and a two-sided 0.05 significance level, 102 individuals will be necessary to detect a 10-point difference between the two groups.

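### Section 16 ties the follow-up result to a 12-week assessment that is not scheduled, and does not say which ODI scale and analysis set decide the trial

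*Combined protocol and SAP*

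**What the plan says.** Section 8.1 defines the primary outcome as functional disability "measured through the Oswestry Disability Index score (patient reported outcome measure) between baseline and 8 weeks". Section 8.2 sets the same interval for the secondary outcomes. Section 15 schedules assessments at baseline, 4 weeks and 8 weeks, and section 14 gives both programmes a length of 8 weeks.

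Section 16 then specifies:

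- Time point and scale: outcomes are assessed "considering both the results at the 12-week assessment as well as change from baseline".
- Sets: "Outcome analysis will be performed using both an intention to treat analysis and a per-protocol analysis".
- Tests: "Differences between interventions will be evaluated using independent samples t test" or Mann–Whitney U; then "Additionally, a repeated measures ANOVA will also be performed", with group and time as factors.
- Level: "In all analysis, a significant level of 0.05 will be considered".

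No scale, test or set is called primary, no rule covers disagreement between them, and no analysis uses baseline ODI as a covariate. Section 9 states that "102 individuals will be necessary to detect a 10-point difference between the two groups", from a baseline SD of 17.83, 80% power and a two-sided 0.05 level. The hypothesis in section 6 is that "The digital program will be associated with at least the same outcomes as conventional PT"; no margin is given.

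**The concern.** There are two defects. First, the SAP names a visit that does not exist, so the follow-up-value analysis cannot be carried out as written. Second, the same ODI data can be analysed on two scales and in two sets, and nothing fixes in advance which result counts. Participants and investigators know the allocation and the ODI is patient-reported. The blinded statistician promised in section 13 does not settle which analysis decides.

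The meaning of a 0.05 result is at stake. If one significant result out of several sufficed, the error rate would exceed 0.05; if several had to agree, it would fall below 0.05 and power would drop. The scale also determines whether 102 participants deliver the stated 80% power.

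**Working it through.** **Time point.** Sections 8.1, 8.2, 14 and 15 all stop at 8 weeks. Apart from section 16, a 12-week period appears only in the pain-duration entry criterion (section 10.1). The 12 in section 16 is most simply a slip for 8.

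**Reproducing N = 102.** Inputs from section 9: difference 10, SD 17.83, two-sided 0.05, power 80%. Allocation 1:1 is assumed, since section 13 does not state a ratio. The two-sample t calculation gives 50.88 per arm, so 51 per arm and 102 in total. With 51 per arm:

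- standard error = 17.83 × √(2/51) = 3.53
- noncentrality = 10/3.53 = 2.83, on 100 degrees of freedom
- power = 80.1%

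The stated N is therefore exact for a t test on a score with SD 17.83, which fits the week-8 value if its SD equals the baseline SD.

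**Power by scale, 51 per arm, complete data.** The correlation r between baseline and week-8 ODI is not in the documents; 0.3, 0.5 and 0.7 are assumed, with equal variances at both visits. The SD to use is:

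- week-8 value: 17.83
- change: 17.83 × √(2(1−r)) = 21.10, 17.83, 13.81
- baseline-adjusted (ANCOVA): 17.83 × √(1−r²) = 17.01, 15.44, 12.73, with one degree of freedom fewer

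| r | Week-8 value | Change | ANCOVA |
|---|---|---|---|
| 0.3 | 80.1% | 65.9% | 83.6% |
| 0.5 | 80.1% | 80.1% | 89.9% |
| 0.7 | 80.1% | 95.2% | 97.5% |

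A change-score test falls short of 80% whenever r is below 0.5, because 2(1−r) then exceeds 1.

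**Error rate if either of two results could be claimed.** Null simulation, 51 per arm, 40,000 replicates per r, t tests, Monte Carlo standard error at most about 0.2 points. Chance of at least one two-sided p < 0.05:

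| Pair of results | r = 0.3 | r = 0.5 | r = 0.7 |
|---|---|---|---|
| Week-8 value or change, ITT | 8.8% | 9.1% | 9.4% |
| Change, ITT or per-protocol | 6.9% | 7.1% | 7.1% |

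The per-protocol set is assumed to be a random 80% of each arm. For comparison, two independent tests would give 1 − 0.95² = 9.75%. If change had to be significant in both sets, the rate would be about 3%.

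**Incomplete data.** Section 9 makes no allowance for attrition, while sections 14 and 15 foresee dropouts and exclusions. With 41 per arm contributing week-8 data (assumed, about 80% of 51):

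- week-8 t test: standard error 17.83 × √(2/41) = 3.94, power about 71%
- ANCOVA: about 75%, 83% and 94% at r = 0.3, 0.5 and 0.7

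**The case against.** The documents do narrow the choice. Section 8.1 fixes one instrument and one interval, and its wording leans to change. The repeated measures ANOVA is introduced as an addition and so reads as supplementary. The choice between t and Mann–Whitney appears to follow normality. The sentence naming both scales speaks of overall impact and could be descriptive; the between-group tests come in a separate sentence. All of this stands, and it limits the open question to scale and analysis set. It does not close it.

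The error rates also need a rule that any significant result may be claimed, and the plan states no such rule. That stands too: 7% to 9% measures what the silence could cost, not the trial's actual error rate. A reader might infer a larger figure by counting the ANOVA, or every test in both sets, as co-deciding. The text does not support that, because it gives the ANOVA an additional role.

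Unadjusted t tests are valid. Naming the t test on week-8 ODI would by itself cure the ambiguity of scale and test and would match N = 102. Baseline adjustment is a gain in precision, about 4 points of power over the week-8 value at r = 0.3 and about 2 over change at r = 0.7.

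Finally, a reader might infer that section 15, which excludes participants who do not complete the forms, contradicts an ITT analysis. The documents do not define ITT, and exclusion from the study may mean withdrawal from follow-up. The supportable statement is that the two sections need clarifying together.

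**Conclusion.** The concern holds on two counts. The 12-week reference is wrong as written. Section 16 also leaves open which ODI scale and which set decide the trial. The second defect would be worth about 7% to 9% against a nominal 5%, but only if either of two results could be claimed, with the per-protocol set an assumed random 80%. Across the assumed correlations, the choice between change and baseline adjustment moves power at N = 102 between 66% and 98%, given complete data and equal variances.

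A reader might infer that 102 is miscalculated; it is not. It reproduces exactly for a week-8 t test, but the 80% is conditional on complete data. The missing margin for the section 6 hypothesis bears on what the deciding analysis tests, but is a separate question. The correction should be made before analysis.

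**What to change.** 1. In section 16, replace the 12-week assessment with the 8-week assessment.
2. Name one primary analysis: week-8 ODI by arm, adjusted for baseline ODI, by ANCOVA or as the week-8 contrast of a mixed model using the week-4 and week-8 scores. Report the mean difference in ODI points with a 95% confidence interval. Label the t and rank tests, the change-score test and the repeated measures ANOVA supportive. Naming one analysis controls the error rate; the covariate adds precision.
3. For a test of difference, make the ITT set of all randomised participants primary. Clarify in section 15 that a participant who misses a form stays in that set and that the available data are used.
4. State that this analysis tests the two-sided difference sized in section 9. If the section 6 claim is the intended one, settle the margin, the sample size and the role of the per-protocol set separately.
5. State in section 9 that the 80% power is conditional on complete data.

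The cost is wording only. Baseline, week-4 and week-8 ODI are already scheduled, so no visit or measure is added.

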##### d) Medication consumption

Measured through the following questions:

- i. "Are you taking any medication for your low back pain?";
- ii. "If yes, are you taking opioids for your low back pain?";
- iii. "If yes, on how many days in a week, on average, are you taking medication for your low back pain"

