### **g) Patient engagement**

Measured through: g.1) adherence to exercise sessions; g.2) drop-out rates; g.3) treatment intensity (i.e. total number of exercise minutes)

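### Section 16 names no between-arm effect measure for the yes/no secondary outcomes, and does not use the baseline medication and opioid answers as covariates

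*Combined protocol and SAP*

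**What the plan says.** Section 8.2 d) asks two yes/no questions, "Are you taking any medication for your low back pain" and, for those who answer yes, "are you taking opioids for your low back pain". A third item in that section, days of medication per week, is numeric. Section 8.2 g) adds "drop-out rates", a yes/no event for each participant. Section 15 collects the outcome items at baseline, 4 and 8 weeks.

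Section 16 opens with a paragraph on clinical and demographic variables of the allocated patients. It gives the t test or Mann-Whitney for quantitative variables and then says "For categorical variables, Chi-square test or Fisher's exact test will be used". Outcome analysis is introduced after that. The outcome text says "Differences between interventions will be evaluated using independent samples t test" or Mann-Whitney, then "For non-normally distributed variables, the magnitude of the difference in the medians will be assessed using Hodges-Lehman estimator". It adds a repeated measures ANOVA with group and time, and log transformation where needed. Results are to be assessed both at the final visit and as change from baseline. (Section 16 calls the final visit week 12, while sections 8 and 15 end at week 8. That is a separate matter, and week 8 is used here.)

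**The concern.** The outcome text names methods for scores only. It gives no risk difference, risk ratio or odds ratio and no model for a binary response. An analyst could defend a t test, Mann-Whitney with Hodges-Lehmann, or chi-square carried over from the opening paragraph. The p-values would be much the same, but the reported effect would not.

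The background section stresses non-opioid alternatives and poor completion of PT programs, so readers will look for an interpretable estimate on these items. Also, baseline use is likely to predict week-8 use. The answer is already collected, yet no planned analysis adjusts for it.

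**Working it through.** **Sample size.** Section 9 gives an SD of 17.83, a difference of 10 points, 80% power and two-sided 0.05. The normal formula gives 2 × (1.96 + 0.8416)² × (17.83/10)² = 2 × 7.849 × 3.179 = 49.9, so 50 per arm. The t-based solution gives 50.9, so 51 per arm and 102 in total, which matches the plan. The documents state no allocation ratio, so 1:1 is assumed. They give no rate for any yes/no outcome, so every rate below is an assumption.

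**Hodges-Lehmann on 0/1 data.** The estimate is the median of all between-arm pairwise differences, each -1, 0 or +1. With p1 > p2, the share of pairs equal to +1 is p1(1 - p2), so the population value is 0 unless p1(1 - p2) > 0.5. For a product of 0.5, the gap p1 + (1 - p2) - 1 is smallest when both factors equal √0.5, giving 2 × 0.7071 - 1 = 0.414. Any true difference below about 41 points therefore gives 0.

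Simulation at 51 per arm (4000 runs for Hodges-Lehmann, 1000 for the tests):

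| True rates | p1(1 - p2) | Share of trials with estimate 0 | Rejection rate: t, Mann-Whitney and chi-square alike |
|---|---|---|---|
| 30% v 10% | 0.27 | 1.00 | 0.740 |
| 50% v 30% | 0.35 | 0.99 | 0.528 |
| 60% v 30% | 0.42 | 0.91 | 0.889 |
| 70% v 30% | 0.49 | 0.59 | 0.988 |
| 80% v 20% | 0.64 | 0.02 | 1.000 |

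The three tests (without continuity correction) rejected equally often, so only the estimate is at issue.

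**Change scores (-1, 0, +1).** Take 30% v 12% stopping and 2% v 4% starting, so 68% v 84% are unchanged. The share of pairwise differences equal to 0 is 0.30 × 0.12 + 0.68 × 0.84 + 0.02 × 0.04 = 0.608. That exceeds one half, so the estimate is again 0.

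**What a risk difference would show.** At 60% v 30%, SE = √(0.24/51 + 0.21/51) = 0.094, so 0.30 (95% CI 0.12 to 0.48). At 50% v 30%, SE = √(0.25/51 + 0.21/51) = 0.095, so 0.20 (0.01 to 0.39).

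**Use of the baseline answer.** Assume 50% use at baseline and 51 per arm.
- Scenario A: 90% v 55% of users persist and 10% of non-users start. Week-8 use is 0.5 × 0.90 + 0.5 × 0.10 = 50% v 0.5 × 0.55 + 0.5 × 0.10 = 32.5%.
- Scenario B: 90% v 50% persist and 5% start. Week-8 use is 0.5 × 0.90 + 0.5 × 0.05 = 47.5% v 0.5 × 0.50 + 0.5 × 0.05 = 27.5%.

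| Analysis | Power, A | Power, B |
|---|---|---|
| Week 8 only, unadjusted | 44% | 56% |
| Mann-Whitney on change (planned) | 58% | 76% |
| Adjusted for baseline answer | 64-66% | 83-84% |

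The gain over the change analysis is 6 to 8 points in A and 7 to 8 in B. Over week 8 alone it is 20 to 22 and 27 to 28. Type I error was 5 to 6% for all three. Repeat runs move single figures by about two points, so only the size of the gain should be read.

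**The case against.** The strongest reply is that section 16 sets a rule by type of variable at the start, with chi-square or Fisher for categorical ones, and that a competent analyst would carry it into the outcomes. The opening paragraph is not limited to baseline in words, and Hodges-Lehmann is tied to differences in medians, which suggests numeric scales. This largely stands: the text leaves a gap and does not assign yes/no items to the wrong test. It does not close the gap, because chi-square and Fisher give a p-value without an effect estimate or interval.

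A reader might infer two stronger claims, and the documents support neither.
- *The plan will report an effect of 0 for almost any true difference.* This needs the Hodges-Lehmann route, which the plan never expressly applies to yes/no items. The t test route gives the difference in proportions, and even Hodges-Lehmann is non-zero for very large gaps.
- *Baseline use is ignored.* Section 16 calls for change from baseline and a repeated measures ANOVA, and both use it. It is only absent as a covariate. Drop-out has no baseline value at all.

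It is also fair to say that the proper comparator for power is the planned change analysis, so the relevant gain is the smaller one. The sample size rests on the ODI, and these are secondary outcomes. Log transformation applies only when necessary, so that it is undefined at 0 is no separate fault.

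**Conclusion.** The point holds as a gap plus a nearly free improvement. Section 16 prespecifies no between-arm effect measure for any medication use, opioid use or drop-out, and one of the routes it leaves open is uninformative for true differences below about 41 points. Week-8 test results would hardly change. Adjusting for the baseline medication or opioid answer is worth about 6 to 8 points of power over the planned change analysis in the two scenarios tried. That gain rests on 51 per arm, 50% baseline use and the assumed persistence and starting rates; it would differ for rarer opioid use. The primary ODI analysis is not affected.

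**What to change.** In section 16, add a paragraph for yes/no outcomes:
- **Medication use and opioid use:** compare arms at 8 weeks with a model that includes the baseline answer to the same question, and report the risk difference with 95% CI. Code participants not on medication as not using opioids, since the opioid question is put only to those on medication. Use Fisher's exact test if counts are too sparse for the model.
- **Drop-out:** report the unadjusted risk difference with 95% CI and Fisher's exact test.
- **Scope:** restrict the t test, Mann-Whitney with Hodges-Lehmann, ANOVA and log transformation to scores and counts.

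The cost is SAP wording only; no new data are needed. The downside is that the model may not converge if opioid use is rare. A logistic fit can also fail when no baseline non-user starts: in scenario B, with about 51 non-users, the chance is 0.95⁵¹ ≈ 7%. The fallback should therefore be written in advance.

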### 15. ASSESSMENTS AND SPECIFIC DATA COLLECTION

Patients will be assessed at baseline, 4 and 8 weeks. All questionnaires will be collected through the EDC system. These will need to be filled within 5 consecutive days. To promote compliance with this schedule, whenever the deadline is approaching, automatic email reminders will be sent to participants. Participants will be excluded from the study for protocol breach in case they don't fill in the assessment forms.

Regarding the **baseline assessment**, participants will be asked to complete the survey before the start of the program. This assessment will include all the information pertaining to the primary and secondary outcomes, as well as the following information:

- a) date of birth
- b) gender
- c) height & weight
- d) body mass index
- e) formal education (years of schooling)
- f) job type
- g) baseline physical activity level
- h) previous back surgery (> 3 months ago)
- i) risk factors: working status, smoking status

For the **4- and 8-week assessment**, participants will be required to complete the questionnaire within a 5-day window beginning at the start of week 4 and 8. These assessments will include all the information pertaining to the primary and secondary outcomes. Physical activity will be measured only at baseline and 8 week assessment.

For participants on the digital group, engagement and usage metrics of the educational and CBT components will also be collected automatically.

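### The added group-by-time ANOVA has no F test that isolates the 8-week arm difference in ODI, and Section 16 does not say which test decides; a baseline-adjusted mixed model would do this better at almost no cost

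*Combined protocol and SAP*

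**What the plan says.** - **Endpoint (Section 8.1):** "Impact on functional disability measured through the Oswestry Disability Index score (patient reported outcome measure) between baseline and 8 weeks".
- **Visits (Section 15):** "Patients will be assessed at baseline, 4 and 8 weeks". Of the 4- and 8-week assessments it says: "These assessments will include all the information pertaining to the primary and secondary outcomes". ODI is therefore measured three times.
- **Between-group test (Section 16):** "Differences between interventions will be evaluated using independent samples t test or Mann–Whitney U test". Outcomes are assessed "considering both the results at the 12-week assessment as well as change from baseline", although Section 15 schedules no 12-week visit.
- **Added analysis (Section 16):** "a repeated measures ANOVA will also be performed, with group as an independent factor and time as a within-subjects factor". The section does not list the levels of time, say which F test is of interest, define a week-8 contrast, or give a sphericity correction.
- **Analysis sets and missing data:** "Outcome analysis will be performed using both an intention to treat analysis and a per-protocol analysis". No missing-data method is given. Section 15 also removes from the study, as a protocol breach, participants who do not complete the assessment forms.
- **Ranking:** the 0.05 level applies to every analysis, and none is named as the deciding one.

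**The concern.** A classical ANOVA on three visits yields three omnibus F tests, and each asks something other than the question in Section 8.1.

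- **Group effect:** compares the arms on the average of all three visits. One of these is the pre-treatment baseline, where randomisation makes the expected difference zero.
- **Group-by-time interaction:** asks whether the arms differ in profile at all. It includes week 8, but a week-4 difference alone can make it significant.
- **Time effect:** pools the arms and carries no arm comparison.

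The classical method also uses only participants with all three visits.

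The ANOVA will be reported beside the t test with nothing to say which prevails. It can therefore be non-significant when the 8-week difference is real, or significant when the arms are equal at 8 weeks. Either result could be read as evidence on the primary endpoint.

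**Working it through.** **Inputs.** From Section 9: SD 17.83, difference 10 points, 80% power, two-sided 0.05, total 102. Section 13 gives no allocation ratio, so I assume 1:1, or 51 per arm. The documents give no between-visit correlation r, so I use 0.3, 0.5 and 0.7. I assume equal variances and equal correlations across visits. Differences are listed in the order baseline/week 4/week 8.

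**The plan's own figure.** SE = 17.83 × √(2/51) = 3.53, and 10/3.53 = 2.83. The two-sample t test (100 df) then has 80.1% power. With 50 per arm it has 79.3%. So 102 is reproduced and is not in dispute.

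**Group effect, differences 0/5/10.** Target = (0+5+10)/3 = 5 points. Variance of a participant's three-visit mean = 17.83² × (1+2r)/3. At r = 0.5 this is 211.9, so SE = 14.56 × √(2/51) = 2.88 and 5/2.88 = 1.73, which gives 40% power.

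**Interaction, 2 and 200 df.** Noncentrality λ = (51/2) × Σ(d − d̄)² / [17.83² × (1−r)], where d is the difference at each visit.
- 0/5/10: the sum is 50. At r = 0.5, λ = 8.0 and power is 71%.
- 0/10/0: the sum is 66.7. At r = 0.5, λ = 10.7 and rejection is 84%. The profiles 0/0/10 and 0/10/10 have the same sum and so the same rejection rate; the test cannot tell them apart.
- 0/5/0: the sum is 16.7. At r = 0.5, λ = 2.7 and rejection is 29%.

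**Tests aimed at week 8, 10-point difference.**
- Change from baseline: SE = 17.83 × √(2(1−r)) × √(2/51) = 3.53 at r = 0.5, power 80%.
- Baseline-adjusted week-8 contrast: SE = 17.83 × √(1−r²) × √(2/51) = 3.06 at r = 0.5, power 90%.

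| Test | Differences | r = 0.3 | r = 0.5 | r = 0.7 |
|---|---|---|---|---|
| Group effect | 0/5/10 | 48% | 40% | 35% |
| Interaction | 0/5/10 | 56% | 71% | 91% |
| Interaction | 0/10/0 | 69% | 84% | 97% |
| Change t test | 10 at week 8 | 66% | 80% | 95% |
| Baseline-adjusted contrast | 10 at week 8 | 84% | 90% | 98% |

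Under 0/10/0 the t tests on week-8 ODI and on change reject in about 5% of simulated trials, as they should. Under 0/5/10 at r = 0.5, the change t test is significant while the group effect is not in about 47% of simulated trials.

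**Complete cases.** The documents give no dropout rate, so this is illustrative. If 10% miss week 4 and, independently, 10% miss week 8, then 102 × 0.9 = 92 have the endpoint but 102 × 0.9 × 0.9 = 83 have all three visits. If everyone who misses week 4 also misses week 8, nothing extra is lost.

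**The case against.** **The ANOVA is only an addition.** The t test or Mann–Whitney test comes first, Section 16 names change from baseline, and the sample size matches a two-group comparison. This stands: a reader might infer that the trial has no test of its 8-week endpoint, and the documents do not support that. But being additional does not settle which result prevails when two unranked tests at 0.05 disagree.

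**Section 16 never calls the group or time effect the treatment test.** Correct. The usual test in such a design is the interaction, so the 40% power and 47% discordance bite only if the group effect is read as the treatment effect. Section 16 does not exclude that reading.

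**The interaction does include week 8.** It does, and it is non-specific rather than blind. The profile 0/5/10 is also its least favourable among those ending at 10 points. For 0/10/10 at r = 0.5 it has 84% power, against 80% for the change t test, so it is not always the weaker test. The 84% rejection with equal arms at week 8 needs a full 10-point week-4 difference that vanishes while both 8-week programmes continue; for 5 points it is 29%.

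**Time might have two levels.** With baseline and week 8 only, the interaction F equals the square of the change t statistic, and the non-specificity disappears. Three levels is the natural reading of Section 15, but it is an inference.

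**Section 15 may already remove anyone who misses a form.** Read literally, the t test would lose those participants too. The complete-case loss therefore cannot be charged to the ANOVA alone.

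**Conclusion.** The point holds as a worthwhile improvement to the analysis, not as a flaw that leaves the primary question untested. On the three-visit reading, no omnibus F test in the planned ANOVA isolates the 8-week arm difference. The group effect halves a 10-point effect that builds linearly. The interaction mixes week-4 and week-8 differences. The size of both problems depends on the assumed correlation and profile. The extra complete-case loss depends on the missingness pattern and can be nil.

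A baseline-adjusted 8-week contrast gains about 18, 10 and 3 percentage points of power over the change t test at r = 0.3, 0.5 and 0.7 (84−66, 90−80, 98−95). That gain comes from the baseline adjustment, which Section 16 does not plan. It is an advantage of the replacement rather than a measure of the ANOVA's fault.

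**What to change.** 1. **Section 16, model.** Replace the ANOVA with a mixed model for repeated measures on ODI at weeks 4 and 8. Include arm, visit, arm-by-visit and baseline ODI, with unstructured covariance, and use all randomised participants with any post-baseline ODI.
2. **Section 16, ranking.** Name the model's 8-week arm difference with its 95% CI as the primary analysis, and label the t test and Mann–Whitney test supportive. Replacing the ANOVA sentence alone would still leave several unranked tests.
3. **Section 16, time point.** Change the 12-week reference to agree with the 8-week endpoint in Section 8.1.
4. **Section 15, missed forms.** Amend the exclusion rule so that a missed form does not remove a participant's other ODI data from the intention-to-treat analysis. Otherwise the model cannot use the participants it is meant to keep.

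If a two-level ANOVA (baseline and week 8) was intended, Section 16 should say so; it would then add nothing to the t test on change.

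The cost is a rewritten paragraph in Section 16 and an amended rule in Section 15. Standard software suffices, the 4- and 8-week ODI are already scheduled, and the sample size of 102 does not change.

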#### 8.2 Secondary Outcomes

The secondary outcomes will include the following, measured between baseline and 8 weeks:

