### **13. ALLOCATION & BLINDING**

Patients will be randomly allocated to one of two groups, using random permuted blocks of 6. After eConsent collection, the investigator will enter the EDC portal and proceed with randomisation (also built into the EDC). Following randomisation, the investigator will contact the person responsible for the rehabilitation program in each group to allocate the participant to the respective study arm. Blinding of investigators and patients regarding allocation arm will not be possible, given the nature of the intervention. Analysis of study results will be performed by a statistician blinded to allocation groups.

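### Section 16 tests 14 named secondary measures, each in several ways, at 0.05 with no decisive analysis and no supportive status; for the roughly 11 that are clean nulls, the chance of a false significant result is about 30% to 57%

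*Combined protocol and SAP*

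**What the plan says.** Section 8.1 names one primary outcome, the ODI. Section 8.2 introduces the rest: "The secondary outcomes will include the following, measured between baseline and 8 weeks". Its nine headings contain 14 separately named measures, before any questionnaire subscales.

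Section 9 sizes the trial on the ODI alone: "Considering a power of 80% and a two-sided 0.05 significance level".

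Section 16 closes with "In all analysis, a significant level of 0.05 will be considered". It also states: "Outcome analysis will be performed using both an intention to treat analysis and a per-protocol analysis". Primary and secondary outcomes alike are to be judged both on the follow-up result and on change from baseline. Groups are compared by t test or Mann–Whitney test, with a repeated measures ANOVA in addition.

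The plan gives no testing order, no multiplicity adjustment, no key secondary outcome and no statement that secondary results are exploratory or supportive.

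**The concern.** A single unadjusted threshold covers many measures, and each measure can be tested in several ways. Some nominally significant secondary result is therefore quite likely by chance alone. Because no analysis is named in advance as the one that counts, a reader of the report could not tell a planned finding from one picked out of several.

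The practical risk is a trial with no ODI difference that nevertheless reports a significant benefit on, say, opioid use, mood or work impairment. Section 13 says that patients and investigators are not blinded, and most of these measures are self-reported, so loose control here deserves attention.

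**Working it through.** **1. The plan's own figure.** Inputs from section 9: difference 10 points, SD 17.83, two-sided 0.05, power 80%. Equal allocation is assumed, since section 13 gives two groups but no ratio. Normal approximation: n per arm = 2 × (1.960 + 0.842)² × 17.83² / 10² = 2 × 7.85 × 3.179 = 49.9, so 50 per arm. The t-based calculation gives 50.9, so 51 per arm and 102 in total (power 80.1%). The stated 102 is reproduced. It spends the full 0.05 on the ODI.

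**2. Count of secondary measures (section 8.2).** Pain 1, WPAI 1, interest in surgery 1, medication 3, FABQ 1, GAD-7 and PHQ-9 2, engagement 3, Net Promoter Score 1, IPAQ 1. Total 14.

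**3. Which are clean nulls under clinical equivalence.** The three engagement measures are not:
- Exercise minutes differ by design: three sessions of 20 to 30 minutes weekly (section 14.1) against two of 30 minutes (section 14.2).
- Drop-out has a different definition in each arm: fourteen days without a session, against four consecutive missed sessions.
- Adherence is measured against a different schedule in each arm.

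This leaves 14 − 3 = 11.

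**4. Which can have a change score.** Of the 11, the Net Promoter Score rates the programme received, so it has no meaningful pre-programme value, although section 15 says that baseline collects all outcomes. This leaves 10.

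**5. One test per measure.** If independent, the chance of at least one false positive is 1 − 0.95^11 = 43.1%. For correlated measures, two-sided z tests were simulated under the null with a common correlation r (200,000 draws), each statistic being √r × shared term + √(1 − r) × own term.

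**6. Follow-up value plus change.** Baseline b was simulated as in step 5. Follow-up was f = ρb + √(1 − ρ²) × a new term of the same structure. Change was (f − b)/√(2 − 2ρ), with ρ the baseline to follow-up correlation. All 11 measures were tested on f and 10 also on change.

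| 11 measures | r = 0 | r = 0.3 | r = 0.5 |
|---|---|---|---|
| One test each, either direction | 43% | 38% | 30% |
| One test each, favouring digital | 24% | 19% | 15% |
| Change added for 10, either direction | 63% | 57% | 48% |
| Change added for 10, favouring digital | 39% | 31% | 25% |

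The lower two rows take ρ = 0.5. Repeat runs, and ρ = 0.7, move them by about one percentage point.

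**7. Sensitivity to the count.** Dropping the Net Promoter Score as well leaves 10 measures. One test each gives 1 − 0.95^10 = 40.1% if independent, and 35% or 29% at r = 0.3 or 0.5. Adding change gives 55% or 47%.

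Per-protocol and ANOVA repeats are not in these figures; counting them as further chances of a significant result can only raise the totals. Subscales, if scored separately, would do the same.

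**The case against.** **Independence is the least plausible case.** Pain, work impairment, fear avoidance, mood and medication use come from the same patients. This stands, and it is why a range is given. A reader might instead count all 14 measures, take 1 − 0.95^14 = 51%, and say that a false finding is as likely as not. The documents do not support that: three of the 14 may differ between arms without any error, and 51% needs independence. Giving all 14 a change score (66% or 55% at r = 0.3 or 0.5) goes wrong in the same way, since four of them describe the programme and have no pre-programme value.

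**The harm described is a false benefit, not any false result.** This also stands. The figures that match that harm are the rows favouring the digital arm, roughly half of the two-directional ones.

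**The outcomes are already labelled.** A reader might infer that the plan lets a significant secondary result count the same as the primary. It does not say so. Sections 8.1 and 8.2 separate the two, section 9 uses the ODI only, and section 16 has no rule that turns a secondary p-value into trial success.

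**Unadjusted secondaries are common practice.** That is fair where they are declared supportive and each has one named analysis. Here neither holds, so the labels alone do not settle how a secondary p-value should be read.

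**Conclusion.** The point holds in a moderate form. Applied as written, section 16 gives unreliable significance statements for the secondary outcomes. For about 11 clean nulls, the chance of at least one false result in either direction is 30% to 43% with one test each. It is about 48% to 57% once change scores are added at correlations of 0.3 to 0.5. False results favouring the digital arm account for about 25% to 31% in that last case.

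These sizes rest on assumptions. The documents give no correlations; those between measures (0 to 0.5) and from baseline to follow-up (0.5, checked at 0.7) are chosen. All tests are treated as normal, which is approximate for the yes/no medication items and for the items asked only after a yes. Section 16 refers to a 12-week assessment whereas sections 8 and 15 use 8 weeks; this needs correcting but does not affect the arithmetic.

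The single primary outcome is not in question here.

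**What to change.** Replace the last sentence of section 16 with:

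> 0.05 two-sided applies to one pre-named ITT analysis of the ODI at 8 weeks. Each secondary outcome has one pre-named ITT analysis, reported as an estimate with 95% CI and treated as supportive, with no claim of significance. Per-protocol and other analyses are sensitivity analyses.

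The sponsor must then name those analyses, because section 16 does not yet choose between follow-up value and change, or between the two-group test and the ANOVA, even for the ODI.

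If claims on a few secondary outcomes are wanted, Holm's procedure on a short named family is an option, not a requirement. Making that family conditional on the primary result would first need a rule for when the primary claim is met. The plan lacks one: section 6 expects outcomes at least as good as conventional PT but gives no margin.

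The change costs only wording, with no extra data, visits or participants. The downside is that fewer secondary results can be called significant. It should be made before any results by arm are seen.
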